5.2.4. Day 21 after first vaccine dose (+/-3 days, vaccine dose 2 given)

The following procedures will be performed at the study unit with study participants present. Sampling will be performed prior to vaccination.

Sampling group A

- Review of health declaration questions in Vaccinate, according to care routine before vaccination.
- Vital parameters: Blood pressure, pulse, temperature, and respiratory rate are measured. If the temperature is \geq 38 degrees, the study participant is rescheduled for vaccination on another day, when the person has been fever-free for at least 48 hours.
- Review of adverse events (AE/SAE/SUSAR).
- Review of concomitant medication (all new drugs, including immunosuppressive/immunoglobulin treatments).
- Sampling for SARS-CoV-2 IgG serology and more detailed analyses of humoral immunity (blood).
- Sampling for humoral immunity (saliva).
- Sampling of clinical laboratory tests including blood count (hemoglobin, white blood cells, and platelets) and differential count (neutrophils, lymphocytes, monocytes, basophils, and eosinophils), liver function (ALAT, ASAT, bilirubin, ALP), and creatinine.

- Sampling of HIV-RNA for HIV-infected individuals.
- Vaccine dose 2 is given (in case of anaphylaxis or other significant side effect likely to be related to Comirnaty, this dose will not be given).
- Study participants remain at the healthcare facility for at least 15 minutes (30 minutes for those with bleeding disorders) after vaccination.
- A diary is given to the study participant/information about the eDiary.

Sampling group B

All procedures are performed at the study unit:

- Review of health declaration questions in Vaccinate, according to care routine before vaccination.
- Vital parameters: Blood pressure, pulse, temperature, and respiratory rate are measured. If the temperature is \geq 38 degrees, the study participant is rescheduled for the vaccine dose injection on another day, when the person has been fever-free for at least 48 hours.
- Review of adverse events (AE/SAE/SUSAR).
- Review of concomitant medication (all new drugs, including immunosuppressive/immunoglobulin treatments).
- Sampling for SARS-CoV-2 IgG serology and more detailed analyses of humoral immunity (blood).
- Sampling for humoral immunity (saliva).
- Sampling of clinical laboratory tests including blood count (hemoglobin, white blood cells, and platelets) and differential count (neutrophils, lymphocytes, monocytes, basophils, and eosinophils), liver function (ALAT, ASAT, bilirubin, ALP), and creatinine.
- Sampling of HIV-RNA for HIV-infected individuals.
- Sampling for analysis of cellular immunity (blood).
- Vaccine dose 2 is administered (in the event of anaphylaxis or other significant side effects likely to be related to Comirnaty, this dose will not be administered).
- Study participants remain at the healthcare facility for at least 15 minutes (30 minutes for people with bleeding disorders) after vaccination.
- A diary is given to the study participant/information about the eDiary.

5.2.5. 2-week follow-up (2-week FU) after the second vaccine dose (+/-3 days)

Sampling group A

All contact between study participants and study staff (research nurse or investigator) can be done remotely by phone (or chat, if the Always Open function is available). Can also be done on site, if it coincides with the study participant's regular visit to the study unit, or if the study participant prefers to be sampled at the study unit). Blood samples can be taken at any of the Karolinska University Laboratory's

sampling units in Stockholm, and saliva samples can be sent in a stamped envelope to Karolinska Institutet:

- Review of the diary (local and systemic reactogenicity).
- Review of adverse events (AE/SAE/SUSAR).
- Review of concomitant medication (all drugs from, including immunosuppressive/immunoglobulin treatments).
- Sampling for SARS-CoV-2 IgG serology and more detailed analyses of humoral immunity (blood).
- Sampling for humoral immunity (saliva).
- Sampling of clinical laboratory samples including blood count (hemoglobin, white blood cells, and platelets) and differential count (neutrophils, lymphocytes, monocytes, basophils, and eosinophils), liver function (ALAT, ASAT, bilirubin, ALP), and creatinine.
- Sampling of HIV-RNA for HIV-infected individuals.

Sampling group B

All procedures are performed at the study unit:

- Review of the diary (local and systemic reactogenicity).
- Review of adverse events (AE/SAE/SUSAR).
- Review of concomitant medication (all drugs from, including immunosuppressive/immunoglobulin treatments).
- Testing for SARS-CoV-2 IgG serology and more detailed analyses of humoral immunity (blood).
- Sampling for humoral immunity (saliva).
- Sampling of clinical laboratory tests including blood count (hemoglobin, white blood cells, and platelets) and differential count (neutrophils, lymphocytes, monocytes, basophils, and eosinophils), liver function (ALAT, ASAT, bilirubin, ALP), and creatinine.
- Sampling of HIV-RNA for HIV-infected individuals.
- Sampling for analysis of cellular immunity (blood), increased blood volume for all patient groups.

5.2.6. 6-week follow-up (6-week FU) after second vaccine dose (+/-3 days; remote contact)

Only remote contact via telephone (or chat, if the Always Open function is available) with the study participant.

- Review of adverse events (SAE/SUSAR, last date of reporting period for these).
- Review of concomitant medication (only immunosuppressive/immunoglobulin treatments).

5.2.7. 3-month follow-up (3 m FU) after second vaccine dose (+/- 2 weeks)

Sampling group A

All contact between study participants and study staff (research nurse or investigator) can be done remotely by phone (or chat, if the Always Open function is available. Can also be done on site, if it coincides with the study participant's regular visit to the study unit, or if the study participant prefers to be sampled at the study unit). Blood samples can be taken at any of the Karolinska University Laboratory's sampling units in Stockholm, and saliva samples can be sent in a stamped envelope to the Karolinska Institute.

- Review of concomitant medication (immunosuppressive/immunoglobulin treatments only).
- Sampling for SARS-CoV-2 IgG serology and more detailed analyses of humoral immunity (blood).
- Sampling for humoral immunity (saliva).
- Sampling for HIV-RNA and HIV-DNA for HIV-infected individuals.

Sampling group B

All procedures are performed at the study unit.

- Review of concomitant medication (immunosuppressive/immunoglobulin treatments only).
- Sampling for SARS-CoV-2 IgG serology and more detailed analyses of humoral immunity (blood).
- Sampling for humoral immunity (saliva).
- Sampling for HIV-RNA and HIV-DNA for HIV-infected individuals.
- Sampling for analysis of cellular immunity (blood).

5.2.8. 6-month follow-up (6 m FU) after second vaccine dose (+/- 2 weeks)

Sampling group A

All contact between study participants and study staff (research nurse or investigator) can be done remotely by telephone (or chat, if the Always Open function is available. Can also be done on site, if it coincides with the study participant's regular visit to the study unit, or if the study participant prefers to be sampled at the study unit). Blood samples can be taken at any of the Karolinska University Laboratory's sampling units in Stockholm, and saliva samples can be sent in a prepaid envelope to the Karolinska Institute.

- Review of concomitant medication (immunosuppressive/immunoglobulin treatments only).
- Sampling for SARS-CoV-2 IgG serology and more detailed analyses of humoral immunity (blood).
- Sampling for humoral immunity (saliva).
- Sampling for HIV-RNA and HIV-DNA for HIV-infected individuals.

Sampling group B

All procedures are performed at the study unit:

- Review of concomitant medication (immunosuppressive/immunoglobulin treatments only).
- Sampling for SARS-CoV-2 IgG serology and more detailed analyses of humoral immunity (blood).
- Sampling for humoral immunity (saliva).
- Sampling of HIV RNA and HIV DNA for HIV-infected individuals.

Sampling for analysis of cellular immunity (blood).

5.2.9. 9-month follow-up (9 m FU) after second vaccine dose (+/- 3 weeks)

New informed consent obtained before study procedure. Sampling group A

All contact between study participants and study staff (research nurse or investigator) can be done remotely by telephone (or chat, if the Always Open function is available. Can also be done on site, if coincides with the study participant's regular visit to the study unit, or if the study participant prefers to be sampled at the study unit). Blood samples can be taken at any of the Karolinska University Laboratory's sampling units in Stockholm, and saliva samples can be sent in a stamped envelope to the Karolinska Institute.

- Written informed consent regarding extended study
- Review of concomitant medication (only newly initiated immunosuppressive/immunoglobulin treatments).
- Note any additional vaccination with Comirnaty or other COVID-19 vaccination in the eCRF (concurrent treatment).
- Ask the study participant about COVID-19
- Sampling for SARS-CoV-2 IgG serology and more detailed analyses of humoral immunity (blood).
- Testing for humoral immunity (saliva).
- Sampling for HIV-RNA and HIV-DNA for HIV-infected individuals.

Sampling group B

All procedures are performed at the study unit:

- Written informed consent regarding extended study
- Review of concomitant medication (only newly initiated immunosuppressive/immunoglobulin treatments).
- Note any additional vaccination with Comirnaty or other COVID-19 vaccination in the eCRF (concurrent treatment)
- Ask the study participant about COVID-19
- Sampling for SARS-CoV-2 IgG serology and more detailed analyses of humoral immunity (blood).
- Sampling for humoral immunity (saliva).
- Sampling for HIV-RNA and HIV-DNA for HIV-infected individuals.
- Sampling for analysis of cellular immunity (blood).

5.2.10. 12-month follow-up (12 m FU) after second vaccine dose (+/- 3 weeks)

Sampling group A

All contact between study participants and study staff (research nurse or investigator) can be done remotely by telephone (or chat, if the Always Open function is available. Can also be done on site, if it coincides with the study participant's regular visit to

the study unit, or if the study participant prefers to be sampled at the study unit). Blood samples can be taken at any of the Karolinska University Laboratory's sampling units in Stockholm, and saliva samples can be sent in a prepaid envelope to the Karolinska Institute.

- Review of concomitant medication (only newly initiated immunosuppressive/immunoglobulin treatments).
- Note any additional vaccination with Comirnaty or other COVID-19 vaccination in the eCRF (concurrent treatment).
- Ask the study participant about COVID-19.
- Sampling for SARS-CoV-2 IgG serology and more detailed analyses of humoral immunity (blood).
- Testing for humoral immunity (saliva).
- Sampling for HIV-RNA and HIV-DNA for HIV-infected individuals.

Sampling group B

All procedures are performed at the study unit:

- Review of concomitant medication (only newly initiated immunosuppressive/immunoglobulin treatments).
- Note any additional Comirnaty or other COVID-19 vaccinations in the eCRF (concurrent treatment).
- Ask the study participant about COVID-19
- Testing for SARS-CoV-2 IgG serology and more detailed analyses of humoral immunity (blood).
- Sampling for humoral immunity (saliva).
- Sampling for HIV-RNA and HIV-DNA for HIV-infected individuals.
- Sampling for analysis of cellular immunity (blood).

5.2.11. 18-month follow-up (18 m FU) after second vaccine dose (+/- 3 weeks)

Sampling group A

All contact between study participants and study staff (research nurse or investigator) can be done remotely by telephone (or chat, if the Always Open function is available). Can also be done on site, if it coincides with the study participant's regular visit to the study unit, or if the study participant prefers to be sampled at the study unit). Blood samples can be taken at any of the Karolinska University Laboratory's sampling units in Stockholm, and saliva samples can be sent in a prepaid envelope to the Karolinska Institute.

- Review of concomitant medication (only newly initiated immunosuppressive/immunoglobulin treatments).
- Note any additional Comirnaty or other COVID-19 vaccinations in the eCRF (concomitant treatment).
- Ask the study participant about COVID-19.
- Testing for SARS-CoV-2 IgG serology and more detailed analyses of humoral immunity (blood).
- Sampling for humoral immunity (saliva).
- Sampling for HIV-RNA and HIV-DNA for HIV-infected individuals.

Sampling group B

All procedures are performed at the study unit:

- Review of concomitant medication (only newly initiated immunosuppressive/immunoglobulin treatments).
- Note any additional vaccination with Comirnaty or other COVID-19 vaccination in the eCRF (concomitant treatment).
- Ask the study participant about COVID-19.
- Testing for SARS-CoV-2 IgG serology and more detailed analyses of humoral immunity (blood).
- Testing for humoral immunity (saliva).
- Sampling for HIV-RNA and HIV-DNA for HIV-infected individuals.
- Sampling for analysis of cellular immunity (blood).

5.2.12. 24-month follow-up (24 m FU) after second vaccine dose (+/- 3 weeks)

Sampling group A

All contact between study participants and study staff (research nurse or investigator) can be done remotely by telephone (or chat, if the Always Open function is available. Can also be done on site, if it coincides with the study participant's regular visit to the study unit, or if the study participant prefers to be sampled at the study unit). Blood samples can be taken at any of the Karolinska University Laboratory's sampling units in Stockholm, and saliva samples can be sent in a stamped envelope to the Karolinska Institute.

- Review of concomitant medication (only newly initiated immunosuppressive/immunoglobulin treatments).
- Note any additional vaccination with Comirnaty or other COVID-19 vaccination in the eCRF (concurrent treatment).
- Ask the study participant about COVID-19.
- Sampling for SARS-CoV-2 IgG serology and more detailed analyses of humoral immunity (blood).
- Testing for humoral immunity (saliva).
- Sampling of HIV-RNA and HIV-DNA for HIV-infected individuals.
- Fecal sampling for HIV patients and controls, for those individuals who have agreed to this part.

Sampling group B

All procedures are performed at the study unit:

- Review of concomitant medication (only newly initiated immunosuppressive/immunoglobulin treatments).
- Note any additional vaccination with Comirnaty or other COVID-19 vaccination in the eCRF (concomitant treatment).
- Ask the study participant about COVID-19
- Sampling for SARS-CoV-2 IgG serology and more detailed analyses of humoral immunity (blood).
- Sampling for humoral immunity (saliva).
- Sampling for HIV-RNA and HIV-DNA for HIV-infected individuals.
- Sampling for analysis of cellular immunity (blood).
- Fecal sampling for HIV patients and controls, for those who have agreed to this part.

5.2.13. 30-month follow-up (30 m FU) after second vaccine dose (+/- 3 weeks)

New informed consent obtained before study procedure. Sampling groups A
and B

All contact between study participants and study staff (research nurse or investigator) can be done remotely by telephone (or chat, if the Always Open function is available. Can also be done on site, if it coincides with the study participant's regular visit to the study unit, or if the study participant prefers to be sampled at the study unit). Blood samples can be taken at any of the Karolinska University Laboratory's sampling units in Stockholm, and saliva samples can be sent in a stamped envelope to the Karolinska Institute.

- Review of concomitant medication (only newly initiated immunosuppressive/immunoglobulin treatments).
- Note any additional vaccination with Comirnaty or other COVID-19 vaccination in the eCRF (concurrent treatment).
- Ask the study participant about COVID-19.
- Sampling for SARS-CoV-2 IgG serology and more detailed analyses of humoral immunity (blood).
- Sampling for humoral immunity (saliva).
- Sampling of HIV-RNA and HIV-DNA for HIV-infected individuals.

Study participants will receive a SARS-CoV-2 antigen test kit for saliva sampling in case of COVID symptoms. Study participants will only contact the research staff if they test positive or need more test kits.

5.2.14. 36-month follow-up (36 m FU) after second vaccine dose (+/- 3 weeks)

Sampling group A

All contact between study participants and study staff (research nurse or investigator) can be done remotely by phone (or chat, if the Always Open function is available. Can also be done on site, if it coincides with the study participant's regular visit to the study unit, or if the study participant prefers to be sampled at the study unit). Blood samples can be taken at any of the Karolinska University Laboratory's sampling units in Stockholm, and saliva samples can be sent in a stamped envelope to the Karolinska Institute.

- Review of concomitant medication (only newly initiated immunosuppressive/immunoglobulin treatments).
- Note any additional vaccination with Comirnaty or other COVID-19 vaccination in the eCRF (concurrent treatment).
- Ask the study participant about COVID-19.
- Sampling for SARS-CoV-2 IgG serology and more detailed analyses of humoral immunity (blood).
- Sampling for humoral immunity (saliva).
- Sampling of HIV RNA and HIV DNA for HIV-infected individuals.
- Fecal sampling for HIV patients and controls, for those individuals who have agreed to this part.

Sampling group B

All procedures are performed at the study unit:

- Review of concomitant medication (only newly initiated immunosuppressive/immunoglobulin treatments).
- Note any additional vaccination with Comirnaty or other COVID-19 vaccination in the eCRF (concurrent treatment).
- Ask the study participant about COVID-19
- Sampling for SARS-CoV-2 IgG serology and more detailed analyses of humoral immunity (blood).
- Sampling for humoral immunity (saliva).
- Sampling for HIV-RNA and HIV-DNA for HIV-infected individuals.
- Fecal sampling for HIV patients and controls, for those who have agreed to this part
- Sampling for analysis of cellular immunity (blood).

If there are too few study participants in group B at this visit, some study participants from group A may be asked to provide group B samples.

Study participants will be given a SARS-CoV-2 antigen test kit to take home/be sent home for saliva sampling in case of COVID symptoms. Study participants will only contact the research staff if they test positive or need more test kits.

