4.2. Endpoints

Primary endpoint:

- Proportion (95% CI) seroconverting to a positive response to SARS-CoV-2 IgG Serology test after two doses of vaccine, measured 2 weeks after the second vaccine dose.

Secondary endpoints:

- Proportion (95% CI) seroconverting to a positive response to SARS-CoV-2 IgG serology after two doses of vaccine, at 3 months and 6 months after the second vaccine dose.
- Proportion (95% CI) experiencing adverse events, with AE/SAE/SUSAR.
- Number and proportion (95% CI) who experience local reactions and systemic reactions.
- Proportion (95% CI) who receive a new diagnosis of SARS-CoV-2 infection through a positive PCR test.

Exploratory endpoints:

- Proportion (95% CI) seroconverting to a positive response to SARS-CoV-2 IgG serology after two doses of vaccine, at 9 months, 12 months, 18 months, 24 months, 30 months, and 36 months after the second vaccine dose. This may mean that patients in routine healthcare have received one or more additional vaccine doses depending on the recommendations of the Public Health Agency of Sweden.
- A more detailed description of humoral and cellular immune responses at baseline and after vaccinations in blood and saliva at time points immediately before the first vaccine dose (day 0), day 10 after the first dose, immediately before dose 2 on day 21, and 2 weeks, 3 months, 6 months, 9 months, 12 months, 18 months, 24 months, 30 months, and 36 months after the second vaccine dose.
- Prevalence of escape mutations in SARS-CoV-2 sequencing in breakthrough infections.
- Occurrence of development/progression of graft versus host disease in allogeneic stem cell transplant recipients.
- Occurrence of biopsy-verified rejection in solid organ transplant recipients.
- Occurrence of viremia (defined as HIV RNA >50 copies/mL) after vaccination in individuals with HIV infection.
- Change in HIV DNA from study start to 3 and 6 months, 9 months, 12 months, 18 months, 24 months, 30 months, and 36 months after the second vaccine dose in individuals with HIV infection.
- Association between oral and gut microbiome and vaccine response in HIV-infected individuals and controls.

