Study visits		X	X	X	X		X	X	X	X	X	X	X	X
Review of health declaration questions in Vaccinate and/or registration in Vaccinate			X		X			X	X	X	X	X	X	X
Sampling of clinical laboratory samples	X ¹	(X) ^{1,2}		X _{1,2}	X ¹									
SARS-CoV-2 sampling serology and humoral immunity (blood and saliva)		X ²	X	X ²	X		X ³	X	X	X	X	X	X	X
Sampling for cellular immunity analyses (blood)		X ²	X	X ²	X		X	X	X	X	X	X		X ¹⁴

Visit no.	Screening	1	2	3	4	5	6	7	8	9	10	11	12	13
Study contacts		d 0	10 d FU (vacc 1)	d 21	2 v FU (vacc 2)	6v FU (vacc 2)	3 months FU (vacc 2)	6 months FU (vacc 2)	9 months FU (vacc 2)	12 months (vacc 2)	18 months (vacc 2)	24 months (vacc 2)	30 months (vacc 2)	36 months (vacc 2)
Time span	0-28 days before visit 1	Day 0	+/-3 days	+/-3 days	+/-3d	+/-3d	+/- 2 w	+/- 3v	+/- 3v	+/- 3v	+/- 3v	+/- 3v	+/- 3v	+/- 3v
Other procedures for both sampling groups A and B														
Informed consent	X								X				X	
Inclusion/exclusion criteria	X	X												
Demographics	X													
Concomitant medication⁴	X	X	X	X	X	X	X	X	X	X	X	X	X	X
Symptom-driven physical examination⁵														
Vital signs⁶		X		X										
15/30 min post-vaccination observation period		X		X										
Handing out of diary		X		X										
Review of diary for local and systemic reactogenicity⁷			X		X									
Collection AE⁸			X	X	X									
Collection SAE/SUSAR⁹			X	X	X	X								
Sampling SARS-CoV-2 PCR test		X ^{2,10}												
Pregnancy test for women of childbearing age (urine)	X ¹¹	(X) ¹¹												
Microbiome samples for HIV-infected individuals and control subjects, if they have agreed to this part (fecal sample)	X ¹²											X ¹²		X ¹²
For HIV-infected individuals, HIV DNA sample	X ¹³	(X) ¹³					X	X	X	X	X	X	X	X
For HIV-infected individuals, HIV RNA test	X ¹³	(X) ¹³		X	X		X	X	X	X	X	X	X	X
Note any additional vaccination with Comirnaty								X	X	X	X	X	X	X
Question about Covid 19								X	X	X	X	X	X ¹⁵	X ¹⁵

Abbreviations: d= day; w= week; m= month; vac= vaccination, FU= follow-up (follow-up time is counted as time after the last vaccination); AE = adverse events, i.e., undesirable medical events; SAE = severe adverse events, i.e., serious undesirable medical events; SUSAR = suspected unexpected severe adverse reaction, i.e., suspected, unforeseen, serious undesirable reactions (SUSAR). Footnote.

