¹ Includes blood count (hemoglobin, white blood cells, and platelets) and differential count (neutrophils, lymphocytes, monocytes, basophils, and eosinophils), liver function (ALT, AST, bilirubin, ALP), and creatinine.

IgG analysis in blood only at screening. If the screening visit is conducted via video contact, these samples will be taken on day 0, before the injection of the first vaccine dose.

² Samples will be taken before vaccination.

³ Blood samples can be submitted at Karolinska University Laboratory's sampling units in Stockholm, and study participants do not need to be at the study unit. Saliva samples can be sent by mail.

⁴ During screening visits, previous medications/treatments are noted in accordance with 5.5.2. All medications are noted during screening visits. During the period from the day of the vaccine dose until 14 days after, all medications are recorded after each vaccine dose. During other periods during the study, only new immunosuppressive/immunoglobulin treatments are noted, in accordance with 5.5.2.

⁵ Targeted examinations for symptoms during the study period, if necessary.

⁶ Blood pressure, pulse, temperature, and respiratory rate are measured.

⁷ Diary is issued on day 0/study participants receive an e-diary.

⁸ AE is monitored from the first and second vaccine doses until 14 days after each vaccine dose.

⁹ SAE/SUSAR is monitored within the period from the first vaccination day to 6 weeks after the second vaccine dose.

¹⁰ Nasopharynx sample on day 0 and, if necessary, in case of COVID-19 symptoms. COVID-19 symptoms are: cough, fever \geq 38 degrees, breathing difficulties, runny nose, nasal congestion, sore throat, headache, nausea, muscle and joint pain, impaired sense of smell and taste, or diarrhea.

¹¹ If the screening visit takes place via video contact, a pregnancy test will be performed on day 0, before the first vaccine dose is administered.

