5.6.5. Concomitant use of other drugs

All simultaneous use of other drugs will be documented in the CRF.

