6.3.4. Analyses of exploratory endpoints

Descriptive analyses of the "Full analysis set population" in subgroups:

- Proportion (95% CI) seroconverting to a positive response to SARS-CoV-2 IgG serology after two doses of vaccine, at 9 months, 12 months, 18 months, 24 months, 30 months, and 36 months after the second vaccine dose, measured in the "Two doses of vaccine population" compared with the control group.
- Humoral and cellular immune response at baseline and after vaccinations in blood and saliva
- Prevalence of escape mutations in SARS-CoV-2 sequencing in breakthrough infections.
- Prevalence of development/progression of graft-versus-host disease in allogeneic stem cell transplant recipients.
- Occurrence of biopsy-verified rejection in solid organ transplant recipients.
- Occurrence of viremia (defined as HIV RNA >50 copies/ml) after vaccination in individuals with HIV infection.
- Change in HIV DNA from study start to 3 and 6 months, 9 months, 12 months, 18 months, 24 months, 30 months, and 36 months after the second vaccine dose in people with HIV infection.
- Oral/intestinal microbiome and vaccine response in HIV-infected individuals and controls.

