11. APPENDIX

11.1 Appendix 1 - List of parameters for screening visits and during the study period for eCRF

A base module is created for all patients, followed by specific modules for each patient group. The "healthy controls" group has its own base module in eCRF.

Base module: All patients (primary population)

Gender:

M/F Age:

Diagnosis for inclusion: (Primary immunodeficiency/HIV/allogeneic stem cell transplantation or CAR T cell therapy/Solid organ transplantation/CLL)

Immunosuppressive treatment in the last 4 weeks prior to inclusion: yes/no Ongoing medication at inclusion:

- Non-immunosuppressive drugs: yes/no, if yes, which ones
- Ongoing immunosuppressive treatment, steroid: yes/no, if yes, for how long
- Ongoing immunosuppressive treatment, non-steroid: yes/no, if yes, which

Patient group 1. Patients with primary immunodeficiency

Primary diagnosis:

Confirmed genetic mutation: yes/no, if yes, which gene?

Other comorbidities relevant to vaccine response: yes/no (if yes, describe)

Malignancy: yes/no, if yes, describe which?

Lung disease: yes/no, if yes, describe which?

Autoimmune disease: yes/no, if yes, describe which? Immunoglobulin treatment: yes/no

Rituximab Yes/No. If yes: When was the last dose?

Patient group 2. Patients with HIV infection

Ethnicity: Caucasian, Black, Oriental, Latin, Other.

HIV diagnosis date:

Latest CD4: date, number, percentage Nadir CD4: date, number, percentage, Latest HIV

RNA:

Opportunistic infection: yes/no, if yes, which infection and date

Number of years of antiviral treatment:

Antiviral treatment: (which)

BMI:

Diet – normal diet/vegetarian/other: [if other, describe]

Antibiotic treatment during the last 3 months: yes/no, if yes, describe which antibiotic and duration.

Patient group 3. Patients who have undergone allogeneic stem cell transplantation/CAR T cell therapy

Primary diagnosis:

Stage of disease at transplantation Type of donor

Stem cell source Conditioning regimens GVHD prophylaxis

Acute GVHD Yes/No and severity Chronic GVHD Yes/No and severity

Ongoing immunosuppression (non-steroidal) Yes/No and type
Ongoing corticosteroid therapy Yes/No, severity, and type of medication Any significant opportunistic infection prior to vaccination (CMV, EBV, adenovirus, invasive fungal disease)
Previous rituximab Yes/No. If yes:
When? Obliterative bronchiolitis Yes/No

Patient group 4. Patients who have undergone solid organ transplantation/CAR T cell therapy

Primary diagnosis: Blood group

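### HIV RNA and HIV DNA are followed to 36 months, but the 3- to 36-month visit rules omit antiretroviral treatment from medication review and conflict with section 5.6.5

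*Combined protocol and SAP*

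**What the plan says.** Section 4.2 lists two exploratory HIV endpoints. The first is "Occurrence of viremia (defined as HIV RNA >50 copies/mL) after vaccination in individuals with HIV infection". It carries no time limit and no condition on treatment. The second is "Change in HIV DNA from study start to 3 and 6 months, 9 months, 12 months, 18 months, 24 months, 30 months, and 36 months", with the time points counted from dose 2. Section 6.3.4 repeats both under descriptive analyses and gives no rule for changes in antiretroviral treatment.

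Medication recording is governed in several places:

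- Section 5.5.2 has treatment for the underlying disease recorded at screening, all new drugs recorded to 14 days after each dose, and after that only newly started immunosuppressive or immunoglobulin treatment.
- Table 2 marks concomitant medication at every visit, but footnote 4 restricts what is collected: "During other periods during the study, only new immunosuppressive/immunoglobulin treatments are noted, in accordance with 5.5.2".
- The visit lists follow the footnote. Sections 5.2.7 and 5.2.8 (3 and 6 months) limit the review to those two drug classes. Sections 5.2.9 to 5.2.14 (9 to 36 months) read "Review of concomitant medication (only newly initiated immunosuppressive/immunoglobulin treatments".
- Section 5.6.5 is unrestricted: "All simultaneous use of other drugs will be documented in the CRF".
- The HIV module in Appendix 1 has a field for the antiviral regimen and one for "Number of years of antiviral treatment". Neither has dates, and there is no item for a stop, switch or interruption. The appendix heading says its parameters cover screening and the study period, but no repeat visit is named for these fields.

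**The concern.** A viraemia endpoint that is open for three years will pick up viraemia from any cause. An obvious competing explanation is a change or interruption of antiretroviral treatment. That an interruption can raise HIV RNA is a general clinical premise assumed here, not protocol text; the plan does treat antiviral therapy as relevant enough to record in the HIV module.

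The reasons given in 5.5.2 for restricting medication recording are the assessment of adverse-event causality and drugs that might affect vaccine efficacy. Neither concerns the HIV endpoints. From 9 months the visits do record further COVID-19 vaccine doses and ask about COVID-19, so exposure is updated while treatment of the underlying infection is not.

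Safety reporting does not fill the gap. AE collection ends 14 days after each dose and SAE collection 6 weeks after dose 2, and both leave out expected worsening of the underlying disease (5.7.1, 5.7.2, 5.9.1, 5.9.2). There is no unvaccinated HIV group against which a background rate could be read. A reader of the final tables would see a count of viraemic participants and could not separate those whose treatment had changed.

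**Working it through.** The plan states no figure on this point, so there is none to reproduce. The check has two parts.

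**1. Samples set against medication rules** (Table 2, footnote 4, sections 5.2.4 to 5.2.14)

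| Visit | HIV RNA | HIV DNA | Medication review in the visit list |
|---|---|---|---|
| Day 21 | yes | no | all new drugs |
| 2 weeks after dose 2 | yes | no | all drugs |
| 6 weeks | no | no | immunosuppressive/immunoglobulin only |
| 3 and 6 months | yes (2) | yes (2) | immunosuppressive/immunoglobulin only |
| 9, 12, 18, 24, 30, 36 months | yes (6) | yes (6) | newly started immunosuppressive/immunoglobulin only |

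HIV RNA samples after dose 1: 2 + 2 + 6 = 10, of which 2 + 6 = 8 fall at visits whose review omits antiretroviral treatment. Follow-up HIV DNA samples: 2 + 6 = 8, all at such visits. Even at day 21 the review asks about new drugs, so a stop would not clearly be captured.

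**2. Illustration of size**

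Input from the documents: planned HIV group of 90 (Synopsis, 5.1.1). Assumed input, not in the documents: a fraction *a* of participants per year with a treatment interruption that leads to HIV RNA above 50 copies/mL. Also assumed: all 90 stay to month 36, and every episode coincides with a sample.

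Proportion with at least one episode over 3 years: P = 1 − (1 − a)³. Expected number: 90 × P.

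- a = 1%: P = 1 − 0.99³ = 0.030; 90 × P = 2.7
- a = 2%: P = 1 − 0.98³ = 0.059; 90 × P = 5.3
- a = 5%: P = 1 − 0.95³ = 0.143; 90 × P = 12.8

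A second illustration works per visit: with an assumed probability q of a treatment-related viraemic sample at each of the 8 late visits, taken as independent, P = 1 − (1 − q)⁸.

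- q = 0.25%: P = 0.020; 1.8 of 90
- q = 0.5%: P = 0.039; 3.5 of 90
- q = 1%: P = 0.077; 7.0 of 90
- q = 2%: P = 0.149; 13.4 of 90

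The two give similar ranges because the assumed rates are of similar size; neither is evidence about the true rate. No comparable illustration is offered for HIV DNA, for which the documents give no effect size.

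**The case against.** Several points on the other side are sound, and they limit the finding.

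- A reader might infer that antiretroviral treatment is recorded once and never again. The documents do not settle that. Section 5.6.5 has all other drug use entered in the CRF, and the Appendix 1 heading extends its parameters into the study period. What stands is a conflict between passages. Neither of the broader passages names a visit for an update or mentions interruptions.
- A reader might infer that treatment status will be unknown. The patients attend regular check-ups at the same hospital (5.1.1) and are followed in routine care (5.3.2), and CRF data come from clinic source documents (7.3). The information is probably recoverable. But 7.3 ties CRF collection to the protocol, and no passage directs that this information be extracted.
- A reader might infer that every switch or interruption becomes an event. It does not: only HIV RNA above 50 copies/mL meets the viraemia definition.
- A reader might infer that the endpoints are meant to test whether the vaccine disturbs HIV control. Section 4.1 contains no such objective, 6.1 calls the study descriptive or exploratory, and 6.3.4 plans description only.
- Knowing treatment status would not make late viraemia attributable to the vaccine. There is no unvaccinated HIV group, and further doses and infections are expected during follow-up (2.1, 2.2). The two HIV RNA samples nearest vaccination do fall at visits with a broader drug review.
- The illustrated counts lean high for a given rate. Consent is renewed at 9 and 30 months, which may reduce retention, and from 3 months onward samples are 3 to 6 months apart, so short episodes can be missed.

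**Conclusion.** The concern holds as a gap and an inconsistency in data collection. At 8 of 10 HIV RNA occasions after dose 1 and 8 of 8 follow-up HIV DNA occasions, the operative visit rules leave antiretroviral treatment out of the medication review, while 5.6.5 and the Appendix 1 heading suggest wider recording. If the visit rules are followed, viraemia or HIV DNA change after a treatment change would be pooled with all other such findings and could not be separated from the CRF. The counts of samples are firm. The figure of about 3 to 13 of 90 participants depends entirely on assumed interruption rates, full retention and complete capture.

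The documents do not support saying that treatment changes will necessarily be reported as vaccine events: that would require such changes to occur and no one to consult the clinic record. Importance is moderate. Two exploratory, descriptive endpoints in one of six groups are affected; the primary and secondary endpoints are not. The change is worth making because it is cheap.

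**What to change.** 1. In the HIV module of the eCRF, at each visit with HIV RNA or HIV DNA sampling, record from the clinic record whether antiretroviral treatment was changed or interrupted since the last visit, with dates. For visits already held, abstract this retrospectively.
2. Amend footnote 4 of Table 2, section 5.5.2 and the 3- to 36-month visit lists to include this item, and bring them and 5.6.5 into line so that one recording rule applies. State in Appendix 1 which fields are repeated and when.
3. In 6.3.4, report viraemia and HIV DNA change overall and, separately, for participants on unchanged and uninterrupted antiretroviral treatment up to the sample in question.

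The cost is one eCRF item for at most 90 participants at existing visits, plus one extra descriptive table. No new samples or visits are needed. The split helps a reader interpret the two endpoints; the report should say that it does not by itself allow attribution to the vaccine.
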